### 3.2.2 Secondary Endpoints

- Safety profile of the AMIA APD Solution Generation System used to treat patients with PD by collecting AEs, SAEs, ADEs, SADEs, incidence of device alarms and vital signs.
- Peritoneal dialysis adequacy will be measured by sample collection and calculation of total  $Kt/V_{urea}$ , occurring one time during weeks 5, 6, 7 or 8 of the Study Treatment Period.

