### **6.5.7 Simulated Treatments**

For simulated treatments, patients will set up the system as they would for a study treatment, but will not connect the patient line or use the generated solution for treatment. During the monthly simulated treatment, the prescriptions will be manipulated to ensure that the patient produce all three glucose concentrations of the Dianeal Low Calcium PD solutions at different time points for testing. Samples will be collected by the clinic nurse or designee and the disposable set will no longer be usable. The simulated treatment will be ended with no treatment performed on the patient and the patient will then remove the remaining components of the disposable set from the system.

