## 7. DATA COLLECTION FOR SAFETY ASSESSMENTS AND REPORTING

### 7.1 Definition of Adverse Events and Device Deficiencies

**Table 5. Adverse Event Term Definition**

Term	Definition
Adverse Event (AE)	Any untoward medical occurrence in a patient or clinical investigation subject administered a product which does not necessarily have a causal relationship with this treatment.
Adverse Drug Reaction (ADR) or Adverse Reaction (AR) /Adverse Device Effect (ADE)	Adverse event related to the use of study product.
Suspected Adverse Reaction (SAR)	Any AE for which there is a reasonable possibility that the product caused the AE. For the purposes of IND safety reporting “reasonable possibility” means there is evidence to suggest a causal relationship between the product and the AE.
Unexpected Adverse Drug Reaction (UADR)	An adverse reaction in which the nature or severity is not consistent with the applicable product information (e.g., Investigator’s Brochure for unapproved

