## 7.2 Safety Reporting

All AEs, PCs and DDs observed by the study personnel or reported by the patient during the course of the study will be documented from the time of signing the ICF through the End-of-Study/ Early Termination Visit.

Any medical condition, that is present at the time that the participant is screened, will be considered medical history and not reported as an AE (see [Appendix 6](#)). Any medical event that is commonly associated with a study participant’s PD therapy will be considered medical history and not reported as an AE (see [Appendix 6](#)). However, if the study patient’s condition/event worsens (change in severity or frequency) at any time during the study, it will be recorded as an AE.

If a definitive diagnosis has been medically established by the physician caring for the patient or by the Investigator, this diagnosis should then be recorded as the AE on the eCRF and the signs and symptoms removed. If a definitive diagnosis has not been medically established, the signs and symptoms should then be recorded as the AEs.

Adverse events that change in severity will be reported at each incidence, but documented only once in the eCRF with the highest degree of severity.

An elective procedure/ surgery that occurs during the course of a study, but is being performed for a documented pre-existing condition and was pre-planned prior to study entry will not qualify as an AE. If, however, the pre-existing condition unexpectedly deteriorates during the study requiring the procedure/ surgery to be performed earlier than planned, the condition for which the procedure/ surgery is being performed will qualify as an AE.

Laboratory and vital sign abnormalities qualify as AEs if medical intervention is required to treat or address the abnormality, if the patient must be discontinued from the study due to the abnormality, or if the Investigator determines the value is clinically significant.

An AE can result from the use of the study product in accordance with the protocol, as well as from an accidental or intentional misuse of the study product or any other treatment error such as unintentional administration or use of another product during the course of the study.

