### **8.5 Each Treatment Day**

Patients will set up and complete a treatment using the AMIA APD Solution Generation System according to their prescribed dialysis regimen.

The following assessments will be completed each day throughout the Study Treatment Period.

1. Collection of concomitant medication information.
  2. Weight pre- and post-dialysis.
  3. Vital signs, before and after each treatment, including seated BP, pulse rate and temperature.
  4. Collection of AEs/ SAEs.
  5. Collection of ADEs and SADEs once the patient is connected to the AMIA APD Solution Generation System.
  6. Collection of AMIA APD Solution Generation System-related PCs/ DDs, which would include functional characteristics (e.g., particulate matter, PD fluid discoloration, leaks, tubing separations), will begin from the time of signing informed consent and will continue throughout the entire Study Treatment Period.
  7. Collection of machine information.
  8. Collection of machine observations.
  9. Chlorine testing performed by patients before each treatment.
- 
- 

10. Collection of diary source data (eDiary).

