l The Principal Investigator or a designee (e.g., sub-investigator) will assess each patient at the Screening Visit and on a weekly basis. At a minimum, this assessment will include evaluation of BP, pulse rate, weight, fluid status and dialysis prescription.

m AEs and SAEs will be collected after the informed consent is signed and will continue to be collected throughout the Study Treatment Period and during the follow-up period of 5-10 days after the last study treatment. Adverse device events and SADEs will be collected from the time of signing informed consent.

n Medications taken during the study will be documented throughout the study and will include a review of all major body systems and renal history (primary etiology of renal disease and current PD prescription).

o Patients will receive device-specific training which will last up to 2 weeks.

p Comprehension and retention testing will occur at the end of the Baseline Period (In-center Training Period) for patients and care partners (if participating). If the patient does not read and understand English, the care partner will assist the patient with comprehension and retention testing.

q The Investigator must reassess the stability of the patient during the Baseline Period (In-center Training Period). Once the clinician concludes that the patient is clinically stable and their PD prescription is stable, then the patient can begin treatment in the home.

r Written confirmation of independent care by patient and care partner (if participating).

s Machine information will include the available code number(s) and a lot/serial number(s) at initial installation and if the device or any of the disposables are changed.

t Machine observations with each treatment will include the following: duration of PD treatments, start and stop times, total UF volume programmed and removed as obtained from machine log, and technical treatment interruptions – machine alarms.

Observation	Screening (approx. 3 weeks)	Baseline Period (In-center Training, approx. 2 weeks) a	Simulated Treatment Visit 1 b	Each Treatment Day c	Treatment Visits 2, 3 and 4 (Treatment weeks 4, 8 and 12, respectively) d	Total Kt/V urea Visit e	Follow-up Period (5-10 days)	End of Study/ Early Termination Visit f

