14.2.2 Classification of Adverse Events

Pre-treatment adverse event – An adverse event that starts between the date of signing the informed consent form (ICF) and the start of the first treatment.

Treatment-emergent adverse event (TEAE) – An adverse event that starts on or after the start of the first treatment.

In case of incomplete information on study treatment or AE onset, events will be classified as treatment-emergent unless there is sufficient data to rule out the possibility that the event started after the start of study treatment application.

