14.2.4 Presentation of Adverse Events

An AE overview summary table will be prepared to include the number of patients reporting an AE, the percentage of patients (%) with an AE, the number of events reported, for the following categories:

1. Any treatment emergent adverse event
2. Treatment-emergent SAEs.
3. Treatment-emergent pre-defined AEs of special interest
4. Treatment-emergent study device-related AEs.
5. Treatment-emergent typical PD-related AEs
6. Treatment-emergent study device-related SAEs
7. Treatment-emergent typical PD-related SAEs
8. Treatment-emergent AEs leading to withdrawal.
9. Treatment-emergent AEs leading to death.

Adverse events will be further tabulated by body system using the MedDRA coded values. The table will display the total number of patients reporting an AE, the percentage of patients (%) with an AE, and the number of events reported by overall, system organ class (SOC), and preferred term. Table summaries will be produced for:

- All treatment-emergent AEs
 - Treatment-emergent AEs leading to withdrawal
 - Treatment-emergent SAEs
 - Treatment-emergent AEs leading to death
 - Treatment-emergent pre-defined AEs of special interest
 - Treatment-emergent pre-defined SAEs of special interest
 - Treatment-emergent AEs by severity
 - Treatment-emergent SAEs by severity
-
- 

- Treatment-emergent AEs by relationship to study product
- Treatment-emergent SAEs by relationship to study product
- Treatment-emergent AEs by relationship to typical PD therapy
- Treatment-emergent SAEs by relationship to typical PD therapy
- Treatment-emergent adverse events in $\geq 5\%$ of patients

Adverse events occurring between informed consent and treatment start (pre-treatment AEs), treatment-emergent adverse events, treatment-emergent SAEs, treatment-emergent adverse events leading to withdrawal, treatment-emergent adverse events related to study device, typical PD therapy, or another Baxter product, and adverse events for patients who died will be listed.

For the SAE listing, the seriousness criteria will also be included in the listing.

If there are less than 5 adverse events in one of the bulleted categories above, then a listing may be created instead of a table for those AEs.

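### The protocol gives two conflicting start points for ADE/SADE collection, and the SAP lists device-related events before first treatment but does not count them in the ADE/SADE tables

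*Protocol*

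**What the plan says.** **Collection.** Protocol 8.5, which applies to each treatment day, has as item 5: "Collection of ADEs and SADEs once the patient is connected to the AMIA APD Solution Generation System". Footnote m to the schedule of events in protocol Appendix 1 says: "Adverse device events and SADEs will be collected from the time of signing informed consent". SAP Appendix 1 carries the same footnote. Item 6 of the 8.5 list starts product complaints and device deficiencies at consent. Sections 8.4 (Baseline) and 8.6 (Simulated Treatment Visit 1) call for AEs and SAEs but do not name ADEs or SADEs; 8.9 (Follow-up) names all four. In a simulated treatment the patient sets up the system "but will not connect the patient line or use the generated solution for treatment" (protocol 6.5.7).

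**Definitions.** Table 5 of the protocol defines an ADE as "Adverse event related to the use of study product". Section 7.2 says AEs, complaints and deficiencies "will be documented from the time of signing the ICF through the End-of-Study/ Early Termination Visit", with the causal relationship of each AE recorded. The secondary safety endpoint is assessed "by collecting AEs, SAEs, ADEs, SADEs, incidence of device alarms and vital signs" (3.2.2), with no start time.

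**Analysis.** SAP 14.2.2 defines a treatment-emergent event as "An adverse event that starts on or after the start of the first treatment". The device row of the overview table in SAP 14.2.4 is "Treatment-emergent study device-related AEs", and the matching SAE row is restricted in the same way. Pre-treatment events go to listings 16.2.7.1.2 (all) and 16.2.7.1.10 (serious).

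**The concern.** ADEs and SADEs are a named secondary endpoint for a system that is plumbed into the home, taught to the patient and set up by the patient before anyone is connected to it. At Simulated Treatment Visit 1 the patient line stays unconnected, so the trigger in 8.5 has not yet occurred, while the trigger in footnote m occurred at consent. Two sites could label the same early injury differently.

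The tables then describe the device's safety profile from first treatment only. Installation, training and the first set-up, when the user is least experienced, contribute no incidence figure to the ADE/SADE results. A patient who leaves in that interval because of a device-related harm could be missing from the adverse-event output altogether.

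**Working it through.** No sample size, alpha or power bears on this point; the study is descriptive. The check sets the texts side by side and then sizes the interval.

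**1. Collection rule.** Section 8.5 starts at connection and footnote m at consent. The footnote says adverse device *events*, a term the protocol does not define; paired with SADEs, it can only sensibly mean ADEs. Because item 6 of the 8.5 list starts deficiencies at consent, 8.5 itself sets a different window for ADEs. The conflict is real.

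**2. Does the conflict lose records?** An ADE is an AE judged related to the product. AEs are collected from consent, and Screening (8.2), Baseline (8.4) and Visit 1 (8.6) each call for AE/SAE collection. A pre-connection event should therefore be recorded with its causality under either rule. What differs is whether it is classed as an ADE or SADE.

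**3. Where a pre-treatment device-related event appears in the SAP.**

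| Output | Covers it? |
|---|---|
| Overview rows in 14.2.4; tables 14.3.1.1.4, 14.3.1.1.7, 14.3.1.3.2 | No: treatment-emergent only |
| Listings 16.2.7.1.5, 16.2.7.1.13, 16.2.7.1.16 (device-related; SUSAR/UADE) | No: treatment-emergent only |
| Listings 16.2.7.1.2, 16.2.7.1.10 (pre-treatment) | Yes, with relationship to study device (14.2.1) |
| Deficiency summary (14.3.2) | Yes, if a deficiency led to the AE; device days run from home installation |

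SAP 14.2.1 also defines patient-years from consent for all AEs, pre-treatment included, but no table in Section 17 is a pre-treatment or all-AE table. Protocol 10.6 plans AE summaries by relationship to study product with no treatment-emergent limit, and SAP Section 12 declares no changes from the protocol.

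**4. Untreated patients.** The Safety Set requires at least one treatment (SAP 7.2) and is the default for tables and listings (SAP 6). Protocol 8.10 and SAP 7.3 both foresee withdrawal after installation because of a device issue. Such a patient, if never treated, is outside the default output.

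**5. Size of the consent-to-treatment interval.** Protocol 3.4 gives 3 weeks of screening, 2 of baseline, 12 of treatment and 5 to 10 days of follow-up.

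- Total: 21 + 14 + 84 + 5 = 124 days (17.7 weeks), or with 10 days of follow-up 129 days (18.4 weeks). This reproduces the stated duration of about 18 weeks.
- Share before first treatment: 35/124 = 28%; 35/129 = 27%.
- For 30 completers, leaving out the one-day correction in the SAP formula: consent-based patient-years are 30 × 124/365.25 = 10.2 to 30 × 129/365.25 = 10.6. Treatment-emergent patient-years are 30 × 89/365.25 = 7.3 to 30 × 94/365.25 = 7.7. The difference is 30 × 35/365.25 = 2.9.

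**6. Size of the installed-but-untreated interval.** The documents do not fix it, so I assume *w* days and compute *w*/(*w* + 84), the share of device-installed days up to last treatment.

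- *w* = 7 (the longest lead allowed for Visit 1): 7/91 = 7.7%.
- *w* = 14 (expected time for installation plus product-water testing, protocol 4.4): 14/98 = 14.3%.
- *w* = 35 (installation on the first day of Screening): 35/119 = 29.4%.

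**The case against.** The strongest reply is that this is a labelling conflict plus an ordinary reporting choice. AEs with causality are captured from consent; tabulating treatment-emergent events and listing earlier ones is common; and with at most 50 patients a reader can count device-related events from the pre-treatment listing. SAP 14.2.4 itself lets a listing replace a table when a category has fewer than 5 events. Harms caused by a malfunction or use error are already tabulated through the deficiency summary, per device day from installation.

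Most of that stands. A reader might infer that sites following 8.5 would not record early device injuries, that these are left out of the endpoint, or that all of them go unreported. The documents do not support this: AE collection with causality runs from consent, the pre-treatment listings carry relationship to device, and the deficiency summary has no treatment-emergent limit. Nor do they establish a lead of 2 to 5 weeks. The two weeks is an expected duration for installation and testing, not a minimum interval, and five weeks would need installation before the home assessment had been completed.

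The reply does not remove the contradiction between 8.5 and footnote m. It also does not supply a count covering installation and first set-up for events not caused by a deficiency. And it does not reach the installed-but-untreated patient, whose withdrawal and primary reason would appear in the disposition output (based on all consented patients, SAP 7.1) but whose adverse event would not appear in the default AE tables or listings.

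**Conclusion.** The point holds as a consistency and reporting gap. The start of ADE/SADE collection is contradictory and must be reconciled. For Safety Set patients, pre-treatment device-related events are listed but get no count, percentage or rate in the ADE/SADE tables; those arising from a deficiency are counted elsewhere. For patients installed but never treated, device-related events fall outside the default tables and listings.

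The uncounted installed interval is about 8%, 14% or 29% of device-installed days if installation precedes first treatment by 7, 14 or 35 days. These are assumptions, with 84 uninterrupted days of treatment, and the last is an extreme. No event rate is given, so the effect on ADE counts cannot be stated. The gap concerns a patient's time before first-ever treatment: SAP 14.2.1 dates treatment from the first enrollment, so events at a later re-installation of an already treated patient count as treatment-emergent. The primary endpoints are unaffected.

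**What to change.** - **Protocol:** state one ADE/SADE collection start in 8.4, 8.5, 8.6 and Appendix 1, consistent with AE and deficiency collection from consent, and use the defined term (adverse device effect) in footnote m.
- **SAP 14.2.4:** add overview rows for pre-treatment and for total (pre-treatment plus treatment-emergent) device-related AEs and SAEs. The total uses the consent-based patient-years already defined in SAP 14.2.1. If a rate is wanted for the pre-treatment row, its denominator is that figure minus the treatment-emergent patient-years.
- **Untreated patients:** report device-related AEs for patients with a home installation but no treatment, at least in a listing of all patients with a home installation.

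The cost is one reconciled collection rule, a few table rows and one listing. No new data are needed, because AEs with causality are already collected from consent. The reported ADE counts may rise slightly.

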**8.6 Simulated Treatment Visit 1 (Before 1st Treatment in the Home, Study Visit 1)**

The following assessments will be completed during Simulated Treatment Visit 1, Study Visit 1.

1. A simulated treatment will be set up by the patient. The dialysis solution generated during simulated treatment will be collected by the clinic nurse or designee from the system in the heater bag and used to evaluate the chemical composition of the final dialysis solution produced by patients using the AMIA APD Solution Generation System compared to the specifications of Baxter's approved Dianeal Low Calcium (2.5 mEq/L) PD Solution.
2. Product water from the WD (pre-sterilizing filters) will also be collected by a clinic nurse or designee and will be tested to confirm that it conforms to ISO standard 13959 for microbiological (including endotoxin) and chemical contamination. Collecting a product water sample involves connecting a container and/ or tubing to the WD and obtaining a sample volume of water from the WD for microbiological and chemical testing. This procedure cannot be performed using the disposable set required for actual treatment setup, since the sterilizing-grade filters will remove additional microbial contamination. The purpose of this procedure is to demonstrate that the WD is functioning appropriately in the patient's home, and since sampling is not dependent upon the user performing the procedure, patients do not have to perform it for the study (decreasing the impact on patients/ nurses).
3. Water from the holding bag (post-sterilizing filters), generated during a simulated treatment will be collected and tested to confirm it does not exceed 0 CFU/mL for bacteria (no growth) and is < 0.03 EU/mL for endotoxins, consistent with Dianeal specifications for sterility. Simulated treatment is prepared by the patient, in the same manner in which actual treatment is prepared (using the disposable set, filters, etc.) Due to the risk of contamination, the holding bag cannot be compromised, particularly since the water needs to be sterile. The purpose of this procedure is to demonstrate that the system functions as intended when used by patients under real-world conditions.
4. Assessment by an Investigator or a designee.

5. Collection of AEs/ SAEs.
6. Collection of AMIA APD Solution Generation System-related PCs and DDs.

### **8.7 Study Visits 2, 3 and 4 (Study Treatment Weeks 4, 8 and 12)**

Study Visits 2, 3 and 4 will occur during Study Treatment Weeks 4, 8 and 12 of the Study Treatment Period, respectively. In addition to the assessments included in Section 8.5, the following assessments will be completed during Study Visits 2, 3 and 4.

1. A simulated treatment will be set up by the patient. The dialysis solution generated during simulated treatment will be collected by the clinic nurse or designee from the system in the heater bag and used to evaluate the chemical composition of the final dialysis solution produced by patients using the AMIA APD Solution Generation System compared to the specifications of Baxter's approved Dianeal Low Calcium (2.5 mEq/L) PD Solution.
2. Product water from the WD (pre-sterilizing filters) will be also be collected by a clinic nurse or designee and tested to confirm that it conforms to ISO standard 13959 for microbiological (including endotoxin) and chemical contamination, and water from the holding bag (post-sterilizing filters), generated during a simulated treatment, will be collected and tested to confirm it does not exceed 0 CFU/mL for bacteria (no growth) and is < 0.03 EU/mL for endotoxins, consistent with Dianeal specifications for sterility. For more information regarding the differences in simulated treatment testing for product water from the WD and for product water from the holding bag, refer to points 2 and 3 in Section 8.6.
3. Assessment by an Investigator or a designee.

After the final Study Treatment Visit, patients are to transition back to treatments with AMIA with Baxter's approved Dianeal Low Calcium (2.5 mEq/L) PD Solution in their home environment and enter a 5-10 day Follow-up Period. Return of all investigational products and study related supplies will be scheduled during this time.

